13.1 Sample size

Total of 120 randomized subjects

AJG533 10 mg group 60 subjects

AJG533 placebo group 60 subjects

Total of 108 subjects evaluable for primary endpoint

AJG533 10 mg group 54 subjects

AJG533 placebo group 54 subjects

[Rationales for the selection]

The primary endpoint of the Japanese Phase II clinical study (AJG533/ET1), or the change in SBM frequency from screening period Week 2 to treatment period Week 1 (n, LSMeans, [SE]) was (n = 38, 5.63 [0.68]) in the AJG533 10 mg group and (n = 40, 2.63, [0.46]) in the placebo group, with an inter-group difference (LSMeans, [SE]) of (3.00, [0.82]). It has been reported that the target of demonstrating the superiority to the control or standard therapy may not be achieved by performing a new study using only point estimates of efficacy from earlier, relatively small studies because of the scale of the study. Further, several methods for setting sample size have been proposed. Therefore, the one-sided 80% confidence interval of the difference between the placebo and AJG533 10 mg groups was calculated and the lower limit of the interval was considered as the difference in the population mean of the study. The standard deviation of each group was specified based on the results of the AJG533/ET1 study.

The lower limit of the one-sided 80% confidence interval was 2.30 for the difference in the change before and after treatment between the placebo and AJG533 10 mg groups. The sample size required for the study was calculated at 54 subjects per group when it was calculated by t-test in unequal variance, assuming that the population standard deviations of the placebo and AJG533 10 mg groups were 2.90 and 4.24, respectively and assuming a two-sided significance level of 5%, statistical power of 90%, and allocation ratio of 1 to 1 (AJG533 10 mg group to placebo group). Therefore, it was decided that 54 subjects per group were necessary for evaluating the primary endpoint. Assuming that 10% of enrolled subjects would prematurely drop out of the study, it was decided that 60 subjects would be randomized to each group in the study, with the total number of subjects being 120.

13.2 Analysis sets

13.2.1 Definitions of analysis sets

The following 3 analysis sets will be defined:

(i) Full Analysis Set (FAS)

The population of all patients who received at least one dose of the study drug and have any observed efficacy data is defined as the "full analysis set (FAS)."

(ii) Per Protocol Set (PPS)

Per protocol set (PPS) is defined as the set of subjects in FAS excluding those who meet any of the following criteria.

- 1) Subjects who do not meet any of the inclusion criteria or meet any of the exclusion criteria
- 2) Subjects who received the study drug with a different drug number from the allocated number
- Subjects with problems including the use of prohibited medications, poor treatment compliance, lost to follow-up, and missing data *)
- *): The detailed criteria for adoption are specified separately in the "Case and Data Handling Standards."

(iii) Safety analysis set

The population of all patients who received at least one dose of the study drug is defined as the "safety analysis set."

13.2.2 Analysis sets to be used for each evaluation

(i) Analysis set for efficacy evaluation

The FAS will be the primary analysis set.

(ii) Analysis set for safety evaluation

Analyses using the "safety analysis set" will be carried out.

13.3 Data Handling

Standards for data handling are stipulated in the separately prepared Statistical Analysis Plan and Case and Data Handling Standards. In principle, efficacy data collected shall be used for summary and analysis.

Missing values of tests or data not adopted after the handling according to the Case and Data Handling Standards and Statistical Analysis Plan shall be excluded from the statistical tests or estimations for evaluation. Missing values of the primary endpoint will be subjected to the sensitivity analysis for the handling of missing data to examine the stability of the study results.

Because the efficacy evaluation will be performed based on the patient diary, efficacy data at each time point will be handled as follows:

1. screening period Defined as a period of 168 hours from 0:00 on Day -15 to 24:00 on Day -9, assuming

Week 1: the date and time of the first dose of the study drug as the starting point (Day +1).

2. screening period Defined as a period of 168 hours from 0:00 on Day -8 to 24:00 on Day -2, assuming

Week 2: the date and time of the first dose of the study drug as the starting point (Day +1).

3. treatment period Defined as a period for 7 days (168 hours), assuming the date and time of the first

Week 1: dose of the study drug as the starting point (Day +1).

4. treatment period: Defined as a period for 7 days (168 hours) from Day 8, assuming the date and time

Week 2 of the first dose of the study drug as the starting point (Day +1).

13.4 Objectives of Analyses

The primary objective of statistical analysis is to indicate the presence/absence of statistical difference in the primary endpoint, change in SBM frequency, between the placebo and AJG533 10 mg groups by calculating the test statistics and significance probability (p-value) of the primary endpoint.

The secondary objective is to estimate the intergroup differences in various endpoints supporting the primary endpoint.

13.5 Analyses about study progress and subject background

13.5.1 Study progress

The disposition of subjects (including completion status, reasons for discontinuance, and treatment period) will be summarized for all the subjects who provided consent. Protocol deviations will be summarized for subjects who received the study drug. In addition, the treatment status will be analyzed and tabulated using the FAS and safety analysis set.

13.5.2 Subject background

The disposition of all the subjects who provided consent and all the analysis sets will be presented. Using the FAS, PPS and safety analysis set, the status of demographic variables and other baseline data in each group will be presented using frequency distribution tables and summary statistics.

13.6 Analyses for efficacy evaluation

Unless otherwise specified, the significance level and confidence interval of two-sided statistical tests will be 5% and 95%, respectively.

13.6.1 Primary endpoint

13.6.1.1 Primary analysis

Primary analysis will be performed in FAS. The primary endpoint will be defined with the following formula based on SBM frequency in treatment period Week 1 of AJG533 and screening period Week 2.

(Change in SBM frequency) = (SBM frequency in Treatment Period Week 1) - (SBM frequency in Screening Period Week 2)

For the analysis, a normal distribution is assumed for "the change in SBM frequency," and the analysis of covariance (ANCOVA) with the SBM frequency for Screening Period Week 2 as the covariate will be applied. The estimated "difference in the change in SBM frequency" adjusted by ANCOVA, standard error, 95% confidence interval, and p-value will be calculated.

Null hypothesis H_{ij0} : $\mu_i = \mu_j$ (i = placebo group, j = AJG533 10 mg group)

Alternate hypothesis H_{ij1} : $\mu_i \neq \mu_j$, where μ is defined as adjusted mean in this section.

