4.2 Inclusion Criteria

Patients who meet all of the following criteria (i) to (ix)

<<At provisional enrollment>>

- (i) Patients with chronic constipation
- (ii) Patients with the mean SBM frequency < 3 per week from at least 6 months before informed consent
- (iii) Patients with at least one of the following symptoms related to SBM from at least 6 months before the informed consent:
 - (a) Straining during at least 25% of defecations;
 - (b) Lumpy or hard stools in at least 25% of defecations; and/or
 - (c) Sensation of incomplete evacuation for at least 25% of defecations.
- (iv) Patients confirmed to have no organic lesion in the large intestine by colonoscopy or radiographic contrast enema in 5 years
- (v) Age: 20 years or older (at the time of informed consent)
- (vi) Gender: Male and female
- (vii) Inpatient/outpatient status: Outpatient
- (viii) Patients who are capable of providing written consent

<<At enrollment>>

- (ix) Patients with SBM frequency* < 6 during the 2-week screening period
- *: Defecation without laxatives/enema or digital evacuation. Defecation within 24 hours after the use of a laxative or rescue medication will not be deemed as SBM in this study.

[Rationales for the selection]

- (ii) and (iii): These criteria were set to exclude rectoanal abnormalities, which are excretory disorder symptoms, based on the Rome III Diagnostic Criteria for Functional Constipation¹⁾.
- (iv): The criterion was set to definitely exclude organic constipation in consideration of safety.
- (v): The age of 20 years or older, at which the consent of individuals is legally effective, was chosen for patients to voluntarily participate in a clinical study.
- (vii): The criterion was set because constipation is mainly treated on an outpatient basis.
- (viii): The criterion was set in compliance with the spirit of the Declaration of Helsinki.
- (ix): The criterion was set to include patients who have mean SBM frequency of less than 3/week immediately before the start of the study drug.

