When 5, 10, or 15 mg of AJG533 or placebo was orally administered in patients with chronic constipation once daily about 30 minutes before breakfast for 14 days in the Phase II clinical study (AJG533/ET1), the primary endpoint, or the change in SBM from screening period Week 2 to treatment period Week 1 increased dose dependently: it was 2.60 ± 2.89 , 3.50 ± 2.96 , 5.66 ± 4.15 , and 5.59 ± 3.51 in the placebo, 5 mg, 10 mg, and 15 mg groups, respectively. The change was comparable between the 10 mg and 15 mg groups and significantly larger in the 10 mg and 15 mg groups than the placebo group. Many of the other efficacy endpoints used as a secondary endpoint showed significant improvement in the 10 mg and 15 mg groups as compared to the placebo group. The mean stool consistency in the 10 mg group as evaluated using the Bristol Stool Form Scale was 2.25 ± 1.11 , 4.00 ± 0.94 , and 4.25 ± 1.03 at screening period Week 2, treatment period Weeks 1 and 2, respectively. These results show that stool consistency at Weeks 1 and 2 was close to 4, which indicates ideal stool consistency.

Safety evaluation showed that none of the groups had any serious or severe TEAE. Although 4 of the 43 subjects (9.3%) in the 5 mg group discontinued the study due to TEAEs, the rate of subjects who discontinued the study due to TEAEs was 2.6% (1/39) in the 10 mg group and 4.9% (2/41) in the 15 mg group, indicating that the rate was not dose dependent. Common TEAEs included abdominal pain and diarrhoea, which were assumed to be an extension of the pharmacologic effect. Their incidence was not correlated with the dose.

TRAEs that developed in more than 1 subject in any group were limited to abdominal pain, diarrhoea, and abdominal distension. There were no other characteristic adverse events of the study drug.

[figure not shown]
Based on these results, the recommended clinical dose of AJG533 was determined to be 10 mg.

(iii) Treatment method and duration of treatment

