13.6.1.2 Secondary analyses

(1) Sensitivity analysis of primary analysis

The same analyses as the primary analysis will be done in PPS.

(2) Adjusted analysis

Adjusted analysis will be performed in FAS by adding any of the following factors to the primary analysis model as a covariate. The items and categories will be reexamined based on the results of the blinded review and presented in the Statistical Analysis Plan.

- 1) Gender
- 2) Age
- 3) BMI [less than 25kg/m², 25kg/m² or higher]
- 4) Binary data on subjects who meet IBS diagnostic criteria and those who do not
- 5) Use of rescue medication in screening period Week 2
- 6) Constipation severity evaluation in screening period Week 2
- 7) Stool consistency as measured by Bristol Stool Form Scale in screening period Week 2

(3) Subgroup analysis

Subgroup analysis using the following items as a stratification factor will be performed. The items and categories will be reexamined based on the results of the blinded review and presented in the Statistical Analysis Plan.

- 1) Gender
- 2) Age
- 3) BMI [less than 25 kg/m², 25 kg/m² or higher]
- 4) Complications
- 5) Medical history
- 6) Binary data on subjects who meet IBS diagnostic criteria and those who do not
- 7) Use of rescue medication in screening period Week 2
- 8) Constipation severity evaluation in screening period Week 2
- 9) Stool consistency as measured by Bristol Stool Form Scale in screening period Week 2

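### The primary ANCOVA is valid and meets its planned power, but it leaves the screening Week 1 SBM count unused; adding that count is an optional, small gain in precision

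*Protocol*

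**What the plan says.** Section 13.6.1.1 defines the endpoint as "Change in SBM frequency) = (SBM frequency in Treatment Period Week 1) - (SBM frequency in Screening Period Week 2", and for its comparison between groups "the analysis of covariance (ANCOVA) with the SBM frequency for Screening Period Week 2 as the covariate will be applied". Summary (6) 1) repeats this model.

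Section 13.3 defines screening Week 1 separately: "Defined as a period of 168 hours from 0:00 on Day -15 to 24:00 on Day -9". Week 2 follows, from Day -8 to Day -2. Both weeks precede enrollment on Day -1 and both count towards entry under section 4.2 (ix): "Patients with SBM frequency* < 6 during the 2-week screening period". The two-week total is also the baseline of a secondary endpoint, the 14-day change in section 13.6.2.2.

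Section 13.6.1.2 (2) plans further adjusted models: "Adjusted analysis will be performed in FAS by adding any of the following factors to the primary analysis model as a covariate". Seven factors are listed and the Week 1 SBM count is not among them. That list may be re-examined at the blinded review. The clause covers the adjusted and subgroup analyses only; the primary model is fixed in the protocol.

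Section 13.1 sizes the trial with an unequal-variance t-test and assumes no gain from a covariate.

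**The concern.** One 7-day count is a noisy measure of a subject's own SBM rate, particularly when entry requires fewer than 6 events in 14 days. A second week of the same measure is already available for every enrolled subject, because eligibility cannot be judged without it. Adjusting for a prognostic pre-randomization variable narrows the confidence interval of the treatment difference without altering the endpoint or what is estimated. If Week 1 predicts the Week 1 treatment count beyond what Week 2 predicts, the plan collects that information and does not use it. What is at stake is a modest amount of precision and power in the single confirmatory comparison. Bias and type I error are not affected.

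**Working it through.** **1. The plan's own figure.** Inputs from section 13.1: difference 2.30, SDs 2.90 (placebo) and 4.24 (10 mg), two-sided 5%, 90% power, 1:1 allocation.

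SE at 54 per arm = sqrt((2.90² + 4.24²)/54) = sqrt(26.39/54) = 0.699. With the Satterthwaite df (about 94) and the noncentral t, power is 90.3% at 54 per arm and 89.7% at 53. So 54 is reproduced, and 54/0.90 = 60 randomized per arm. This calculation involves no covariate.

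**2. What a second covariate does.** Let r be the partial correlation of the Week 1 count with the outcome, given Week 2 and treatment. The residual variance is multiplied by (1 - r²). The extra covariate costs one df, which with 108 subjects inflates the variance by about 105/104, so the SE rises by sqrt(105/104) - 1 = 0.5%. The protocol gives no value for r; 0 to 0.3 is an assumption.

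| r | Variance cut (r²) | Net change in SE | Net power at 54 per arm |
|---|---|---|---|
| 0 | 0% | +0.5% | 90.0% |
| 0.1 | 1% | 0.0% | 90.3% |
| 0.2 | 4% | -1.6% | 91.1% |
| 0.3 | 9% | -4.2% | 92.5% |

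The break-even is near r = 0.1. Before the df cost, 90% power would need 54, 53, 52 and 49 per arm respectively.

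**3. What r could plausibly be.** Assumed model: subject rates gamma-distributed with mean 1.5 to 2.5 per week before truncation, weekly counts Poisson given the rate, entry only if the two-week total is below 6, and residual variation matched to the planned SDs (pooled sqrt((2.90² + 4.24²)/2) = 3.63).

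- Treatment-week count rises 1:1 with the underlying rate: variance cut 0 to 1.5%.
- It rises 2:1: 0 to 6%.
- Response proportional to the rate, calibrated to the Phase II mean changes of 2.60 and 5.66: about 2% when the rates have a coefficient of variation (CV) of 0.3, and about 7 to 8% at CV 0.5. Other calibrations of this proportional model reach 11% at CV 0.5.

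At CV 0.5 the entry cap leaves the two weekly counts almost uncorrelated (about -0.13 to -0.01), so Week 1 does not merely repeat Week 2. An 8% cut gives a net power of about 92.2%.

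**4. Whether Phase II narrows the range.** Section 7.1.3 reports changes in the placebo, 5, 10 and 15 mg groups of "2.60 ± 2.89 , 3.50 ± 2.96 , 5.66 ± 4.15 , and 5.59 ± 3.51". Section 13.1 gives LSMeans "n = 38, 5.63 [0.68]) in the AJG533 10 mg group and (n = 40, 2.63, [0.46]) in the placebo group", with an SE of the difference of 0.82.

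- Unadjusted SE from the section 7.1.3 SDs: sqrt(4.15²/38 + 2.89²/40) = 0.814.
- Unadjusted SE from the section 13.1 SDs: sqrt(4.24²/38 + 2.90²/40) = 0.827.

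The reported 0.82 lies between them. Whether adjustment gained anything in Phase II therefore depends on which printed SDs are used. For a Week 2 SD of 1.1 to 1.2 (an assumption in line with the simulated counts) and n = 78, the slope of the change on Week 2 has an SE of about 3.63/(1.1 × sqrt(78)) = 0.37 down to 3.63/(1.2 × sqrt(78)) = 0.34. That is a 95% interval of roughly ±0.7, too wide to choose among the settings in step 3.

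**The case against.** The strongest case against acting is that nothing is broken. The covariate is pre-specified, is the endpoint's own baseline and keeps the model to one covariate. The sample size assumed no covariate gain, so the plan delivers the power it states. All of this stands.

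The design also gives some reason to prefer Week 2. Under section 9.1.1 laxatives are prohibited only from the start of screening, and section 10.2 still records their use on Day -16, the day before Week 1 begins. Week 1 is thus the week closest to laxative withdrawal and may say less about the subject's settled rate. This stands as a reason why r could be close to zero. It does not make adjustment biased.

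Two stronger readings are tempting. A reader might infer from the Phase II standard errors that adjusting for Week 2 achieved nothing, and that Week 1 would therefore cut the variance by 6 to 14%. The documents do not support this. Section 13.1 does not say that the Phase II LSMeans were adjusted for baseline, and the comparison changes direction with the SD used. In the simulated model, a slope of change on Week 2 near zero also needs a strong response to the underlying rate: about 4 to 5 more SBMs per unit of rate at CV 0.5, averaged over both arms including placebo. A reader might also infer that adding Week 1 cannot lose anything, or that the single covariate has no advantage. Both are too strong, given the 0.5% SE cost at r = 0 and the simplicity of the planned model.

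The point that does not stand is that the unseen SAP may settle the matter. The blinded-review clause does not reach the primary model.

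**Conclusion.** The omission is real, but it is a missed opportunity and not a defect. The primary analysis is valid, unbiased and adequately powered as planned. Under the stated gamma-Poisson assumptions, adding the Week 1 count lowers the residual variance by roughly 0 to 8%, which puts power at about 90 to 92.5% against 90.3%. Larger gains arise only if response is strongly proportional to the underlying rate. If Week 1 is uninformative, power is about 90.0%. The possible gain of about two points outweighs a possible loss of about 0.3 points, but its size cannot be established from the protocol because no Week 1-outcome correlation is given. The plan should not be described as underpowered or wrongly analysed on this account.

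**What to change.** Optional. In section 13.6.1.1 and Summary (6) 1), state the primary model as ANCOVA of the change in SBM frequency with the screening Week 2 and screening Week 1 counts both as covariates. Leave the endpoint (change from Week 2) and the treatment contrast as they are, and report the Week-2-only model as a sensitivity analysis. Carry the same wording into the SAP.

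The change must be fixed before key code breaking; made afterwards, it would be a data-driven choice of primary model. If the sponsor holds individual Phase II data with the same two screening weeks, the partial correlation can be estimated there first, and the change dropped if it is about 0.1 or less.

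The cost is one sentence in each place, one degree of freedom and no new data. The sample size can stay at 54 evaluable per arm.

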13.6.1.2 Secondary analyses

(1) Sensitivity analysis of primary analysis

The same analyses as the primary analysis will be done in PPS.

(2) Adjusted analysis

Adjusted analysis will be performed in FAS by adding any of the following factors to the primary analysis model as a covariate. The items and categories will be reexamined based on the results of the blinded review and presented in the Statistical Analysis Plan.

- 1) Gender
- 2) Age
- 3) BMI [less than 25kg/m², 25kg/m² or higher]
- 4) Binary data on subjects who meet IBS diagnostic criteria and those who do not
- 5) Use of rescue medication in screening period Week 2
- 6) Constipation severity evaluation in screening period Week 2
- 7) Stool consistency as measured by Bristol Stool Form Scale in screening period Week 2

(3) Subgroup analysis

Subgroup analysis using the following items as a stratification factor will be performed. The items and categories will be reexamined based on the results of the blinded review and presented in the Statistical Analysis Plan.

- 1) Gender
- 2) Age
- 3) BMI [less than 25 kg/m², 25 kg/m² or higher]
- 4) Complications
- 5) Medical history
- 6) Binary data on subjects who meet IBS diagnostic criteria and those who do not
- 7) Use of rescue medication in screening period Week 2
- 8) Constipation severity evaluation in screening period Week 2
- 9) Stool consistency as measured by Bristol Stool Form Scale in screening period Week 2

13.6.2 Secondary endpoints

The belowmentioned endpoints will be analyzed using the FAS and PPS.

- 13.6.2.1 Change in SBM frequency from screening period Week 2 to treatment period Week 2

 The change in SBM frequency will be determined for each subject to calculate summary statistics by groups.
- 13.6.2.2 Change in SBM frequency from the screening period to the treatment period

 The change in SBM frequency for 14 days will be determined for each subject to calculate summary statistics by groups.
- 13.6.2.3 Changes in CSBM frequency from screening period Week 2 to treatment period Week 1 and Week 2

The change in CSBM frequency will be determined for each patient to calculate summary statistics by groups.

- 13.6.2.4 Change in CSBM frequency from the screening period to the treatment period

 The change in CSBM frequency for 14 days will be determined for each subject to calculate summary statistics by groups.
- 13.6.2.5 Proportion of patients who experience spontaneous bowel movements within 24 or 48 hours after the start of the study drug

The rate of subjects who experience spontaneous bowel movements within 24 or 48 hours after the first dose will be calculated by groups to test the difference between the groups by χ 2 or Fisher's exact test.

13.6.2.6 SBM and CSBM responder rates for treatment period Weeks 1 and 2

Each responder rate and its 95% confidence interval will be calculated for each treatment group.

